7.1.1.2 Drug–Adverse Event Relationship

The causality relationship of study drug to the AE will be assessed by the Investigator as either:

Yes or No

If there is a reasonable suspected causal relationship to the study medication, i.e., there are facts (evidence) or arguments to suggest a causal relationship, drug–event relationship should be assessed as **Yes**.

The following criteria should be considered in order to assess the relationship as **Yes**:

- Reasonable temporal association with drug administration

- It may or may not have been produced by the patient's clinical state, environmental or toxic factors, or other modes of therapy administered to the patient
- Known response pattern to suspected drug
- Disappears or decreases on cessation or reduction in dose
- Reappears on rechallenge

The following criteria should be considered in order to assess the relationship as **No**:

- It does *not* follow a reasonable temporal sequence from administration of the drug
- It may readily have been produced by the patient's clinical state, environmental or toxic factors, or other modes of therapy administered to the patient
- It does not follow a known pattern of response to the suspected drug
- It does not reappear or worsen when the drug is re-administered

7.1.1.3 Serious Adverse Events [Immediately Reportable to Roche]

A serious AE (SAE) is any experience that suggests a significant hazard, contraindication, side effect or precaution. These must be reported to Roche within 24 hours of the Investigator becoming aware of the event through the eSAE page in the eCRF. An SAE is any adverse event that at any dose fulfills at least one of the following criteria:

- Is fatal; (results in *death***; NOTE: death is an outcome, not an event)
- Is life-threatening (NOTE: the term "life-threatening" refers to an event in which the patient was at immediate risk of death at the time of the event; it does not refer to an event which could hypothetically have caused a death had it been more severe)
- Required in-patient hospitalization or prolongation of existing hospitalization
- Results in persistent or significant disability/incapacity
- Is a congenital anomaly/birth defect
- Is medically significant or requires intervention to prevent one or other of the outcomes listed above.

**The term sudden death should be used only when the cause of a cardiac origin as per standard definition. The term death and sudden death are clearly distinct and must not be used interchangeably.

Deaths that occur during the protocol-specified AE reporting period (see Section 7.2.1) that are attributed by the Investigator solely to progression of advanced BCC will be recorded only on the Study Discontinuation eCRF. All other on-study deaths, regardless of attribution except PD, will be recorded as an SAE on the AE eCRF and expeditiously reported to the Sponsor.

The study will comply with all local regulatory requirements and adhere to the full requirements of the ICH Guideline for Clinical Safety Data Management, Definitions and Standards for Expedited Reporting, Topic E2 ([Appendix 4](#)).

After informed consent, but prior to initiation of study medications, only SAEs caused by a protocol-mandated intervention will be collected (e.g., SAEs related to invasive procedures such as biopsies, medication washout, or no treatment run-in).

7.1.1.4 Other Safety Findings Requiring Expedited Reporting

Other safety findings may require expedited reporting depending on local legislation.

The following events are events of special interest and will need to be reported to the Sponsor expeditiously (see Section 7.1.2 for reporting instructions), irrespective of regulatory seriousness criteria:

7.1.2 Pregnancy and Lactation

Small-molecule inhibitors of the Hedgehog pathway are known teratogens that result in midline malformations, such as holoprosencephaly, cyclopia, and other severe developmental defects. The teratogenic potential of vismodegib has been confirmed in an embryo-fetal development study in rats (please see the updated Vismodegib Investigator Brochure). Women who plan to become pregnant (during a study or for 9 months after the last dose *or within the designated window per approved local prescribing information for vismodegib [where available], whichever is longer*) are excluded from all vismodegib clinical studies. Please refer to the Vismodegib Investigator Brochure for further information regarding the teratogenic potential of vismodegib.

- Pregnant women: Vismodegib is contraindicated in pregnant women or women planning to become pregnant during treatment and for 9 months *or within the designated window per approved local prescribing information for vismodegib (where available), whichever is longer, after the last dose.*
- Nursing mothers: Vismodegib is contraindicated in nursing mothers. The extent to which vismodegib or any of its metabolites are excreted in breast milk is not known.

7.1.2.1 Use in Women of Childbearing Potential

As of the data cutoff date of 15 December 2011, there have been no reports of pregnancy in female patients treated with vismodegib.

To prevent pregnancy and the risk of fetal exposure to vismodegib, female patients should not become pregnant or plan to become pregnant during treatment with vismodegib and for 9 months *or within the designated window per approved local prescribing information for vismodegib (where available), whichever is longer, after the last dose.*

Specific actions are required when treating female patients of childbearing potential. Patients should be thoroughly counseled and informed of the teratogenic potential of vismodegib. All pregnancy prevention measures for women of childbearing potential must be followed for the duration of the study and for 9 months *or within the designated window per approved local prescribing information for vismodegib (where available),*

whichever is longer, after the last dose. Patients should be counseled on the use of contraception before beginning treatment with vismodegib. As appropriate, the treating physician should refer the subject to her gynecologist or other healthcare provider to ensure proper understanding of the use of her chosen contraceptive method. Acceptable contraception and duration of contraceptive use should comply with locally approved vismodegib (Erivedge[®], the trade name for vismodegib) Pregnancy Prevention Program or prescribing information where vismodegib is commercially available.

Please refer to [Appendix 2](#) for a definition of women of childbearing potential and a list of acceptable and unacceptable forms of contraception.

Women of childbearing potential are required to have a negative medically-supervised serum or urine pregnancy test (sensitivity of at least 50 mIU/mL) within 7 days prior to the first dose of vismodegib. Every 4 weeks thereafter, medically supervised serum or urine pregnancy tests are required for women of childbearing potential, and the test must be negative within 7 days prior to receiving her supply of vismodegib capsules.

Treating physicians must confirm (with documentation in the medical record) a negative pregnancy test and non-childbearing status (both outlined above), that the patient is using two acceptable forms of contraception, that the patient understands the risk of teratogenicity with vismodegib, and that the patient has signed the informed consent understanding the pregnancy prevention program.

Patients must notify the treating physician if they have changed their forms of contraception from the previous month.

If a woman of childbearing potential believes that her contraceptive method has failed, she must immediately stop taking vismodegib, notify her treating physician immediately, and discuss available management options. For female patients outside of the United States, the patient should immediately consult with her physician or obstetrician/gynecologist (OB/GYN) regarding options for pregnancy testing, management, and treatment.

7.1.2.2 Male Patients

It is not known if vismodegib that may be present in seminal fluid would cause teratogenic effects in a fetus born to the female partner of a male subject. Therefore, sexually active male patients must utilize a barrier form of contraception, even if he has had a vasectomy, during vismodegib treatment and for 2 months *or as per approved local prescribing information for vismodegib (where available), whichever is longer*, after the last dose.

7.1.2.3 Pregnancy Reporting

If a female patient becomes pregnant while receiving investigational therapy with vismodegib or within 9 months *or within the designated window per approved local*

prescribing information for vismodegib (where available), whichever is longer, after the last dose, the Investigator must report all pregnancies immediately i.e., no more than 24 hours after learning of the event to the Sponsor.

A female patient must be instructed to stop taking the test “drug” and immediately inform the Investigator if she becomes pregnant during the study. The Investigator should report all pregnancies immediately i.e., no more than 24 hours after learning of the event to the Sponsor, using the *Clinical Trial Pregnancy Reporting Form*. The Investigator should counsel the patient, discussing the risks of continuing with the pregnancy and the possible effects on the fetus. Monitoring of the patient should continue until conclusion of the pregnancy. Pregnancies occurring up to 9 months *or within the designated window per approved local prescribing information for vismodegib (where available), whichever is longer, after the completion of the study medication must also be reported to the Investigator.*

If a female partner of a male patient becomes pregnant during vismodegib treatment or within 2 months *or within the designated window per approved local prescribing information for vismodegib (where available), whichever is longer, after the last dose of vismodegib, the pregnancy must be reported to the Investigator and the Sponsor and alert the female partner to consult with her physician. The partner should be counseled and the risks of continuing the pregnancy discussed, as well as the possible effects on the fetus. Monitoring of the female partner should continue until conclusion of the pregnancy.*

NOTE: The Investigator should fill out a *Pregnancy Reporting Form* only if the pregnant partner has signed a *Pregnant Partner Data Release Form*.

7.1.3 Abortion, Congenital Anomaly and Birth Defects

Abortions, congenital anomalies and birth defects are events of special interest and will need to be reported to the Sponsor immediately i.e., no more than 24 hours after learning of the event (see Section 7.1.2 for reporting instructions).

Abortion, whether therapeutic or spontaneous, should always be classified as serious (as the Sponsor considers these medically significant), recorded on an SAE eCRF page, and reported to the Sponsor immediately i.e., no more than 24 hours after learning of the event.

Any congenital anomaly/birth defect in a child born to a female patient or female partner of a male patient exposed to the investigational product should be recorded and reported as an SAE to the Sponsor immediately i.e., no more than 24 hours after learning of the event.

7.1.4 Blood Donation

Patients must not donate blood or blood products while on study and for 9 months *or as per approved local prescribing information for vismodegib (where available), whichever is longer*, after discontinuation of vismodegib. Where vismodegib is commercially available, avoidance of blood donation should comply with locally approved prescribing information.

7.1.5 Progression of Underlying Malignancy

Progression of underlying malignancy is not reported as an AE if it is clearly consistent with the suspected progression of the underlying cancer, as defined by RECIST criteria or other criteria as determined by protocol. Hospitalization due *solely* to the progression of underlying malignancy should *not* be reported as an SAE. Clinical symptoms of progression may be reported as AEs if the symptoms cannot be determined to be exclusively due to the progression of the underlying malignancy, or do not fit the expected pattern of progression for the disease under study.

Symptomatic deterioration may occur in some patients. In this situation, progression is evident in the patient's clinical symptoms, but is not supported by the tumor measurements. Or, the disease progression is so evident that the Investigator may elect not to perform further disease assessments. In such cases, the determination of clinical progression is based on symptomatic deterioration. These determinations should be a rare exception, as every effort should be made to document the objective progression of underlying malignancy.

If there is any uncertainty about an AE being due only to the disease under study, it should be reported as an AE or SAE.

7.1.6 Treatment and Follow-Up of Adverse Events (AEs)

After the five Safety Follow-Up Visits 1 month, 3 months, 6 months, 9 months, and 12 months from the last dose of study drug continue to follow up AEs as follows:

Related SAEs are to be reported indefinitely.

Related AEs. Follow until one of the following occurs:

- Resolved or improved to baseline
- Relationship is reassessed as unrelated
- Death
- Start of new anti-cancer regimen
- Investigator confirms that no further improvement can be expected
- Clinical or safety data will no longer be collected, or final database closure

Unrelated severe or life threatening AEs. Follow until one of the following occurs:

- Resolved or improved to baseline

- Severity improved to Grade 2
- Death
- Start of new anti-cancer regimen
- Investigator confirms that no further improvement can be expected
- Clinical or safety data will no longer be collected, or final database closure

Unrelated Grade 1 or Grade 2 AEs. Follow until 30 days from the last dose of study drug.

The final outcome of each AE must be recorded on the eCRF.

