5.7.1 Adverse Event-Related Pharmacokinetic Assessments

Patients will have blood draws for adverse event–related PK testing if any adverse events that were reported to be related to vismodegib treatment continue to be present at least 6 months after the last dose of vismodegib. Site personnel must ensure that a thorough review of all ongoing adverse events that have been recorded in the medical chart and eCRF is performed with the patients at the 6 months Safety Follow-up Visit to ensure that all required PK samples are collected. Blood samples (5 mL each) for the adverse event-related PK testing will be collected at the 6, 9, and 12 months Safety Follow-Up Visits.

The total volume of blood loss for adverse event-related PK assessments will be approximately **15 mL** throughout the duration of the study.

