7.2 HANDLING OF SAFETY PARAMETERS

7.2.1 Recording and Collection of Adverse Events

Information about all AEs, whether volunteered by the patient, discovered by Investigator questioning, or detected through physical examination, laboratory test, or other means, will be collected on the Adverse Event eCRF page, documented in the patient's medical records, and followed as appropriate.

All AEs and SAEs, regardless of the relationship to the trial drug, will be recorded in the eCRF.

All AE reports should contain a brief description of the event, date and time of onset, date and time of resolution, intensity, treatment required, relationship to trial drug, action taken with the trial drug, outcome, and whether the AE is classified as serious.

All AEs experienced after the patient has started study treatment must be recorded on the AE form of the eCRF, as well as all new AEs experienced during the study and during further five Safety Follow-Up Visits 1 month, 3 months, 6 months, 9 months, and 12 months after the last dose of study treatment (± 5 days). SAEs considered related to study drug are to be reported indefinitely.

A pre-existing medical condition that is present at the start of the study should be recorded on the Medical History eCRF.

Worsening and/or progression of advanced BCC should not be recorded as an AE or SAE. These data will be captured as efficacy assessment data only.

If a female patient becomes pregnant while receiving investigational therapy or within 9 months *or within the designated window per approved local prescribing information for vismodegib (where available), whichever is longer*, after the last dose of investigational product, the Investigator should report to the Sponsor immediately within one working day (24 hours) of learning of the pregnancy.

Abortion, whether therapeutic or spontaneous, should always be classified as serious (as the Sponsor considers these medically significant), recorded on the eCRF, and expeditiously reported to the Sponsor.

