
AET02
	
Output ID: t_ae_out_ongo_AEMUS_*
 
 
● Analysis Population: Safety-Evaluable Patients, 12 Months FU Complete Subset
 
● Column Variables: Disease status (Locally Advanced, Metastatic)
 
● Column Totals: Total of non-missing Disease status
 
● Analysis Variables: MedDRA System Organ Class, MedDRA Preferred Term.
 
● Numeric Precision and Formatting of Statistics: Use standard display in the mockup
 
● Optional Subsetting: For each System Organ Class and Preferred Term, include sub-grouping for:             
 
○ Resolved
 
○ Resolved with SequelAE
 
○ Ongoing
 
○ Fatal
 
○ Unknown
 
○ Missing
 
 
 

---------------------	--

Programming Notes:

- Only ongoing "Muscle Spasm" Adverse Events at the time of discontinuation are included.
- Patients, who took commercial Vismodegib (according to the Concomitant Medication CRF page) between treatment discontinuation and 12 months after treatment and had ongoing Adverse Events at treatment discontinuation, have been excluded.

Summary of Alopecia AEs Ongoing at the Time of Discontinuation (Collapsed AEs), and Still Ongoing at Last Assessment by Preferred Term, Excluding Patients with Commercial Vismodegib

Output Id : t\_ae\_out\_ongo\_AEAL\_\*

Repeat output t\_ae\_out\_ongo\_AEMUS\_\* for “Alopecia” adverse event.

Summary of Ageusia AEs Ongoing at the Time of Discontinuation (Collapsed AEs), and Still Ongoing at Last Assessment by Preferred Term, Excluding Patients with Commercial Vismodegib

Output Id : t\_ae\_out\_ongo\_AEAG\_\*

Repeat output t\_ae\_out\_ongo\_AEMUS\_\* for “Ageusia” adverse event.

Summary of Dysgeusia AEs Ongoing at the Time of Discontinuation (Collapsed AEs), and Still Ongoing at Last Assessment by Preferred Term, Excluding Patients with Commercial Vismodegib

Output Id : t\_ae\_out\_ongo\_AEDY\_\*

Repeat output t\_ae\_out\_ongo\_AEMUS\_\* for “Dysgeusia” adverse event.

Summary of Weight Decreased AEs Ongoing at the Time of Discontinuation (Collapsed AEs), and Still Ongoing at Last Assessment by Preferred Term, Excluding Patients with Commercial Vismodegib

Output Id : t\_ae\_out\_ongo\_AEWG\_\*

Repeat output t\_ae\_out\_ongo\_AEMUS\_\* for “Weight Decreased” adverse event.

Number of Patients reporting TEAEs (Enrolled Population):

STREAM Template	Description

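### Protocol 7.1.6 sets a 30-day follow-up limit for unrelated Grade 1–2 AEs that conflicts with its own lead-in and with AE collection to month 12, and the SAP has no rule for counting the events affected

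*Protocol*

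**What the plan says.** Protocol Section 7.1.6 opens by naming the five Safety Follow-Up Visits, and its lead-in ends "12 months from the last dose of study drug continue to follow up AEs as follows". A list by AE class follows. Related SAEs are reported without time limit. Related AEs and unrelated severe or life-threatening AEs are followed until one of several endpoints is met. The last class reads "Unrelated Grade 1 or Grade 2 AEs. Follow until 30 days from the last dose of study drug". The section closes with "The final outcome of each AE must be recorded on the eCRF", and makes no exception for any class.

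Protocol Section 7.2.1 states "All AEs and SAEs, regardless of the relationship to the trial drug, will be recorded in the eCRF". It requires entry of every AE after the start of treatment, "as well as all new AEs experienced during the study and during further five Safety Follow-Up Visits", the last of which is at month 12. Table 1 footnote 18 sets the same span. Section 5.3.4 lists AEs among the assessments at each safety follow-up visit.

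The SAP (Adverse Events) specifies several resolution outputs. One family, in 12-month completers, is titled in the style of "Summary of Alopecia AEs Ongoing at the Time of Discontinuation (Collapsed AEs), and Still Ongoing at Last Assessment" and is produced for muscle spasm, alopecia, ageusia, dysgeusia and weight decreased. A broader table, `t_ae_out_c_*`, covers all preferred terms. Two listings show AEs ongoing at treatment discontinuation and still ongoing at the time of analysis, one for patients last consented to protocol version 1 or 2 and one for version 3 or higher. None of these filters on relatedness or grade.

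**The concern.** A list that starts to apply after month 12 cannot sensibly contain a limit that expired about 11 months earlier. A site reading the 30-day line literally could stop updating an unrelated Grade 1–2 AE at day 30. A site reading the lead-in, or working from Sections 5.3.4 and 7.2.1, would keep asking about it to month 12. Both could claim to follow the protocol.

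What is at stake is the description of reversibility. The SAP gives it real attention: it defines a population for potentially reversible AEs and restricts that population to version 3 or higher because earlier versions had only 1 month of follow-up. If one class of AE is in practice followed for 30 days inside the 12-month design, an event that resolved at month 3 could be displayed as persisting, and the share displayed that way would depend on which passage the site used.

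**Working it through.** No plan figure is at issue, so there is none to reproduce. The check is a comparison of passages, a timing calculation and a sensitivity range.

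**1. Timing.** With 30.4375 days per month (the SAP's own conversion for exposure) and the protocol's ±5-day window:

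- month 1: 30.4 ± 5, about days 25–35
- month 3: 91.3 ± 5, about days 86–96
- month 6: 182.6 ± 5, about days 178–188
- month 9: 273.9 ± 5, about days 269–279
- month 12: 365.25 ± 5, about days 360–370

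Day 30 falls inside the month-1 window. Four of the five visits come after it, and 365.25 − 30 leaves about 335 days of AE collection beyond the limit.

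**2. Consistency within 7.1.6.** The lead-in places the list after month 12, the 30-day line places its end at month 1, and the closing sentence requires an outcome for every AE. The first two cannot both have effect. The third cannot be met at day 30 for an event still open then, unless an unresolved status is accepted as final. In addition, follow-up of a related AE may end when it is reassessed as unrelated. A Grade 1–2 event reassessed after day 30 then enters a class whose limit has already passed.

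**3. Route into the SAP outputs.** A collapsed AE takes its outcome from the record with the latest end date. The SAP does not say what happens to a record that has no end date because follow-up stopped.

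- `t_ae_out_c_*` and the five-term tables have rows for Ongoing, Unknown and Missing, so an unfollowed event could fall in any of the three.
- `t_ae_byout_*` has neither an Unknown nor a Missing row.
- The listings of AEs still ongoing at analysis could pick up an open record that was never updated. This matters for the version 3 or higher listing. In the version 1 or 2 listing, follow-up was 1 month in any case.

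**4. Where the effect is small.** Muscle spasms (68%), alopecia (64%), dysgeusia (51%) and weight loss (46%) were the four most common AEs in the earlier pivotal phase II trial of vismodegib (Protocol 1.1.2.2). Section 7.1.1.2 makes a known response pattern a reason to judge an event related. Most events in the five-term tables should therefore be classed as related and not fall under the 30-day line.

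**5. Size, by assumption only.** Let u be the share of tabulated events that are unrelated, Grade 1–2 and unresolved at day 30. Let r be the share of those that resolve by month 12. Let a be the share of those resolved events whose record was left as Ongoing. The excess shown as Ongoing is u × r × a. With a = 1:

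- u = 2%, r = 30%: 0.02 × 0.30 = 0.6 points
- u = 5%, r = 50%: 0.05 × 0.50 = 2.5 points
- u = 10%, r = 70%: 0.10 × 0.70 = 7.0 points
- u = 20%, r = 90%: 0.20 × 0.90 = 18.0 points

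With a = 0, because sites kept following or coded Unknown or Missing, the excess is 0. The documents give none of u, r or a.

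**The case against.** The strongest reply is that the 30-day line is an empty remnant. Read with its lead-in, the list governs only the time after month 12, when a 30-day limit adds nothing. Until then AEs are assessed at every safety visit and each needs a final outcome. At sites taking PK samples, Section 5.7.1 adds a check at month 6: "Site personnel must ensure that a thorough review of all ongoing adverse events that have been recorded in the medical chart and eCRF" must be carried out with the patient. Section 7.2.1, for its part, concerns the recording of new AEs and says little about updating old ones, so the clash with it is partly indirect. The primary safety variables in Section 8.1.1 do not include time to resolution, and incidence, type and severity are untouched.

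Much of this stands, and it limits the point. A reader might infer that follow-up of these events definitely ends at day 30 and that they therefore remain Ongoing in the 12-month tables. The documents do not support that: the lead-in points the other way, no passage says an unfollowed event keeps the outcome Ongoing, and Unknown and Missing are available in the main resolution tables. A reader might also take a new unrelated AE at month 6 as an example of the distortion. It shows the conflict in the text, since its follow-up limit would precede its onset. It does not enter these outputs, because AE summaries default to onset within 30 days of last dose, and the five-term tables and ongoing-AE listings take only events already open at treatment discontinuation.

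The reply does not remove the contradiction in 7.1.6, which sites must interpret, or the absence of an SAP rule for an event with no late assessment.

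**Conclusion.** Section 7.1.6 is internally inconsistent and conflicts with AE collection to month 12. Where a site applied the 30-day limit, an unrelated Grade 1–2 AE open at day 30 lacks a 12-month outcome and may be displayed as Ongoing. The outputs most exposed are `t_ae_out_c_*` and the version 3 or higher listing of ongoing AEs. The five-term tables should be little affected, on the assumption that most of those events are judged related. `t_ae_out_c_*` is not itself specified as a 12-month table, and its population combinations are in the list of planned outputs, which is not part of these documents.

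No numerical bias should be quoted as a finding. The range of 0.6 to 18 points rests wholly on assumed inputs, and the lower bound is 0. That the 30-day line survives from the earlier 1-month follow-up is plausible but not stated anywhere. The point is worth correcting because the correction is cheap and the plan reports reversibility deliberately; it does not threaten the primary incidence results.

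**What to change.** **Protocol.** Reconcile Section 7.1.6 with Section 7.2.1 and Table 1 footnote 18 so that one follow-up end applies to each AE class and the lead-in agrees with the list. Which end applies is for the sponsor to decide.

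**SAP.**

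- Present the resolution tables by relatedness, or restrict the 12-month persistence tables to AE classes that are followed to month 12.
- Count an unrelated Grade 1–2 AE as Ongoing only if an assessment after day 30 confirms it. Otherwise count it as Unknown / not followed beyond day 30. Moving every such event open at day 30 into that row would be wrong, because it would mislabel events that were followed and did persist.
- State how relatedness is carried into a collapsed record, which the current derivation does not mention, and whether the class uses the maximum grade or the grade at day 30.
- Add the same row to `t_ae_byout_*`.

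**Cost.** One extra split or row in the tables and a short derivation rule. The protocol change needs ethics review under Section 13 where local rules require it. All patients are already enrolled, so outcomes already missed cannot be recovered. For those, the SAP rule limits how they are displayed but does not supply the missing information.
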